## 8f. Study Acceptability

Diet Acceptability: An appropriate instrument with known psychometric properties to systematically assess acceptability of specific diets could not be identified in the literature. Therefore, we developed and piloted a simple five-item assessment for this purpose. From a pre-test, Chronbach's alphas were 0.89 and 0.87 for weeks four and ten, respectively, indicating high internal consistency among questionnaire items.

Two versions of the diet acceptability will be utilized in this study. The Diet Acceptability Long Form includes the five-item assessment of diet acceptability along with five items associated with blood glucose management and hypoglycemia relative to the study diet. This form will be used to assess acceptability of diet at Measurement Visits 2, 3, and 4. The Diet Acceptability Short Form includes only the five questions relative to study diet acceptability. Participants will be asked to respond to this form approximately one month after beginning a study diet period (months 1, 4, and 7).

Overall study acceptability will be ascertained at the conclusion of the intervention period. Study staff will conduct an exit interview with study participants to gather feedback on the study, including intervention design, process, and education materials.

## 9. ACTION SMART Pilot Intervention

### 9a. SMART Pilot Overview

Intervention Arms: Through the sequential randomization process, three evidence-based diets will be evaluated. Diets were selected purposefully to vary substantially in macronutrient composition and in whether or not calories are explicitly restricted.

Diet 1: Look AHEAD (hypocaloric): The Look AHEAD "intensive lifestyle intervention" will be followed, except that the calorie prescription will be T1D-specific and individualized based on findings from energy balance modeling in Phase 1 Study 1, calculated to attain the Look AHEAD weight loss goal of 7% body weight loss/1 year. The caloric distribution will be <30% fat, <10% saturated fat, and ≥15% protein.

Diet 2: Low Carbohydrate (hypocaloric): We will implement a low carbohydrate diet similar to the diet described by Tay et al.,(2015) which resulted in significant weight loss and improved metabolic status with no adverse impact on LDL cholesterol in patients with T2D over 12 months. The caloric distribution will be: 15-20% from carbohydrate, 22-27% from protein, with fats being at least 37% monounsaturated fat and <10% as saturated fat). Individualized calorie goals will be established in the same manner as for Diet 1.

Diet 3: Healthy (Mediterranean) Dietary Pattern (not calorically restricted): This approach is justified by the PREDIMED diet, which employed Mediterranean diets without caloric restriction and resulted in reduced weight and waist circumference

among people with T2D, despite supplementation with either olive oil or nuts. Current ADA guidelines also support use of healthy dietary patterns such as the Mediterranean diet. In patients with T1D, common current clinical practice for weight loss is to advise reduced consumption of energy dense, nutrient poor foods and encourage consumption of healthy foods with ongoing carbohydrate counting for glycemic management. Diet 3 will use this approach and clarify appropriate food choices consistent with PREDIMED dietary guidance, but without the direct provision of olive oil or nuts, which is not practical. Dietary guidance includes: (1) abundant use of olive oil for cooking and dressing; (2) increased consumption of fruits, vegetables, legumes and fish; (3) reduction in total meat consumption, recommending white meat instead of red or processed meat; (4) preparation of homemade sauce with tomato, garlic, onion, and spices with olive oil to dress vegetables, pasta, rice and other dishes; (5) avoidance of butter, cream, fast food, sweets, pastries and sugar-sweetened beverages; and (6) in alcohol drinkers, moderate consumption of red wine.

### 9b. SMART Pilot Procedures

***All RD sessions are conducted remotely following the restrictions placed on in person visits due to COVID-19.***

The initial counseling session, following baseline measurement but prior to initial randomization, will be designed to explore the participant's past experiences with both glycemic control and weight management. An overview of healthy diet and general concepts related to weight management will be discussed. Motivational interviewing will be used to facilitate discussion of the participant's perceptions of challenges and strengths related to diabetes self-management, including glycemic control, dietary choices, and weight management. Problem-solving skills training will be initiated. This initial session will establish the MI/PSST process, which will be used for all diets. Depending on results of Phase 1 Study 2 project on hypoglycemia, this initial counseling session will incorporate a discussion of problem-solving related to dietary response to hypoglycemia. Because self-monitoring will be used for all diets, we have designed a simple, one-week run-in period during which participants will monitor carbohydrate grams and weight. Participants will be shown how to use "MyFitnessPal," an app commonly used by individuals with T1D for carbohydrate counting. Participants will also be provided with a Body Trace scale for home use. This scale transmits weight using the cellular network, through which we can confirm self-monitoring.

Further virtual counseling sessions will provide specific instruction and ongoing MI and PSST related to dietary adherence and glycemic control in the context of diet assignment. Self-monitoring of dietary intake and weight as relates to goal setting and attainment will be reviewed, and problem-solving skills developed to address barriers to adherence will be encouraged. The participant will be queried and any difficulties related to blood glucose management in the face of the experimental diet will be addressed.

Periodic shorter phone check-in sessions will focus on review of goal attainment and problem-solving strategies.

For an overview of measurement and intervention contacts, see Figure 9.1.

### 9c. Intervention Components

**Behavioral Framework for Dietary Interventions:** We will deploy the behavioral framework established and refined by the FLEX study team as an adaptive method to help individuals accomplish individualized goals that improve self-management. Theories of health behavior, and analysis and integration of theory in social and health psychology, suggest a conceptual framework positing knowledge, motivation, and skills as necessary for behavior change. Our application of this theory is to integrate motivational interviewing (MI) and problem-solving skills training (PSST) approaches into a coherent intervention and to supplement these with pragmatic tools tailored to overcome specific barriers to adherence. MI, an effective, patient-centered approach to health behavior change, is used to help individuals resolve ambivalence about change and to enhance intrinsic motivation by creating a motivational frame for change. Once this motivation for change is achieved, PSST, a systematic approach to problem-solving, is presented as a way to make desired changes.

**Registered Dietitian (RD) Counseling:** Shown in Figure 9.1, RDs will conduct 18 sessions over 10.5 months: 8 longer virtual counseling and education sessions and 15 phone “check-in” sessions, a framework similar to the ADA guidelines for intensive lifestyle counseling for weight management. Study RDs will be centrally trained and certified to deliver the proposed intervention, including use of the MI and PSST counseling strategies, and delivery of education related to adherence to the specified experimental diets. All RD sessions will be documented, including audio-recording of the in-person sessions to enable ongoing assessment of fidelity of intervention delivery. For all 3 diets, self-monitoring of diet and weight will be encouraged in the context of individual goal-setting. Participants will be encouraged to continue on with their usual level of physical activity throughout the study, as this study is focusing on changes to diet. Counseling related to glucose management and physical activity will be provided as needed, and carbohydrate counting will be reinforced for insulin dosing. Participants on the low carbohydrate diet will learn about necessary insulin dosing adjustments related to higher protein and fat intake. The participants will be queried and any difficulties related to blood glucose management in the face of the experimental diet will be addressed.

**Intervention Materials:** The study team developed intervention materials for each of the study diets. Materials will utilize motivational interviewing (MI) techniques and problem solving skills training (PSST). MI is a collection of patient-centered interviewing techniques that can be used as the context for virtually any psychological or behavioral intervention. MI is designed to create a collaborative environment in which patients can develop arguments for change, understand and resolve their ambivalence to change, develop strategies for change, and increase their confidence in their coping abilities. PSST teaches problem-solving as a behavior process through which individuals can accomplish the task of self-management.

The initial RD session focuses on providing an overview of healthy eating strategies, reviewing use of MyFitnessPal and the BodyTrace scale, use of nutrition labels, and an introduction into PSST strategies. Additional intervention sessions will utilize study diet materials to teach use of the specific diet to help the study participant achieve a healthy

diet within the guidelines of the specific study diet. Materials will include guidance on insulin dosing, caloric intake (for the two hypocaloric study diets), self-monitoring of dietary intake and weight, modification of a typical daily intake to meet guidelines of the specific study diet, use of nutrition labels, and PSST to identify specific goals within the context of use of the study diet in day-to-day life. Additional materials to be provided include guidance for eating out, recommendations for exercise for individuals with T1D, sample meal plans for each of the study diets, guidance for alcohol intake for individuals with T1D, and recognition of signs and symptoms for hyperglycemia, hypoglycemia, and diabetic ketoacidosis.

*Fidelity:* All full-length intervention sessions will be audio-taped. Fidelity assessment will include review using a content fidelity checklist. Initially, the first two of each session type (initial, introduction to each diet, follow-up to each diet) by each RD will be reviewed. A random sample of other sessions will be reviewed in a timely fashion to provide feedback to the interventionists throughout the intervention.

## 10. Data management

An online data management system utilizing CDART from the Collaborative Studies Coordinating Center will be developed for this SMART pilot. The system will include online data collection and tracking of participant randomization. CDART has robust security features including unique user logins with expiration dates and complex password requirements; storage of hashed passwords only; granular permissions based on user requirement; and encrypted data transmission. The secure server environment where the systems that host CDART reside is located within a hardened data center on the UNC campus, and is governed by standard UNC information security guidelines. Weekly vulnerability detection scans are performed by a third-party vendor, which include full administrative credentials to perform maximum detection techniques. Real-time virus protection software is implemented, and weekly full system virus scans are performed. Daily backups of the data are made and stored in an off-site location. CDART is 21 FDA Part 11 compliant.

Upon entry into the study, a unique identifying number will be assigned to each participant. This number will be used to identify the information and specimens collected and stored during this study. Specimens collected and transferred to the central laboratory will have no identifier other than the unique identifying number assigned to the participant. The roster containing the unique identifying number and direct participant identifiers will be kept in a local password-protected database on a secure network drive at the clinical sites.

## 11. Statistical Considerations

We will primarily compare the 3-month response rates to each of the three initial diets using standard statistical comparison procedures (e.g., t-tests and ANOVA) for differences in glycemic control (HbA1c and percent time in hypoglycemia) and change

in weight. In addition, we will conduct a series of secondary, hypothesis-generating analyses using standard statistical approaches as well as more complex fixed and mixed effect regression methods such as generalized additive models and random forests for these outcomes plus body fat and fat free mass. We will compare all diet sequences (there are 12) using the same outcomes and will incorporate evaluation of measures of ingestive behaviors. After adjusting for multiple comparisons, the proposed sample size of n=84 is sufficient to ensure 60% power to detect a moderate effect size (Cohen h=0.68) and 80% to detect a large effect size (Cohen h=0.85) at a significance level of 0.10 for comparing response rates among the 3 diets. Based on data reported in Wing et al (2016) and Russell et al (2014) and other preliminary data, we estimate for the same significance level and with 80% power that we will be able to detect a difference of about 3.0kg for weight change, 1.3% for HbA1c change, and 1.3 percentage point change in percent time <70mg/dl. Here we emphasize that, by design, our primary goal for this pilot work is to inform the final efficacy design, and we have therefore not designed this pilot SMART to be fully powered for all analyses.

An advantage of SMARTs is that they allow for efficient estimation of precise (i.e., deeply tailored) diet strategies. A precise diet strategy adapts treatment to the evolving health status of each participant. We will use a regression-based approximate dynamic programming algorithm known as Q-learning to estimate the precise diet strategy that maximizes weight loss while improving suboptimal or maintaining good glycemic control over the duration of the trial. The form of this estimated optimal diet strategy will generate hypotheses about how best to choose and adapt diets to individual patients. This will require the use of SMART analysis methods for balancing competing outcomes.

For treatment assignment, permuted block randomization with blocks of size 24 will be used to assign all 12 potential treatment regimes using R statistical software. This will be confidentially generated by the statistician and placed into CDART software to be revealed only at the point of treatment (diet) assignment for each patient. The 12 possible regime sequences are (1,2,2), (1,2,3), (1,3,2), (1,3,3), (2,1,1), (2,1,3), (2,3,1), (2,3,3), (3,1,1), (3,1,2), (3,2,1), and (3,2,2). To illustrate, suppose a patient is assigned treatment sequence (1,3,3). Then, at baseline, only the initial diet (Diet 1) will be revealed. At 3 months, if the response is positive, the patient will continue with the same diet (Diet 1) for the next 3 months to the 6-month follow-up time. If at 6 months the patient is not responding, the new diet (Diet 3) will then be revealed. At 6 months, if the patient response is positive, the patient will continue with the most recently assigned diet (either Diet 1 or 3 depending on the outcome at 3 months yielding one of the two treatment paths (1,1,1) or (1,3,3)). If, at 6 months, the patient response is not positive, the new diet will be revealed. The new diet is Diet 3 if the patient had a positive response at 3 months (yielding the diet sequence (1,1,3)), otherwise the patient will receive the only unused diet, Diet 2 (yielding the diet sequence (1,3,2)). Thus a single regime will provide for four treatment paths depending on patient response. Moreover, all treatment assignments remain hidden in CDART until it becomes time to reveal the new diet. We recognize that patients who do not respond at either the 3 or 6 month time points will be able to anticipate their third diet, but all other patients will not. This is as unblinded as possible for this open label setting.

Effect sizes with accompanying confidence intervals will be estimated using mean outcome at 3 months and standard ANOVA methods will be used for confidence interval construction. We have no reason to think that diets will be differentially acceptable or effective for men compared to women; however, exploratory analyses will consider sex differences in response to the three diets.

We also note that there are 21 possible diet sequences, but there are only 12 treatment regimes based on the randomization scheme. The distinction between regimes and sequences is described in Chapter 2 of *Adaptive Treatment Strategies in Practice: Planning Trials and Analyzing Data for Personalized Medicine* (Kosorok and Moodie, 2016), but this can be illustrated by example. One treatment regime is the following: treat initially with Diet 1, then, if the patient responds favorably after 3 months, continue with the same diet, otherwise switch to Diet 3. After 6 months, if the patient responds favorably, continue with the same diet as given in the previous period. Otherwise, if they were on Diet 1, switch to Diet 3; If they were on Diet 3, switch to Diet 2. Although this is a single treatment regimen (reflecting a single treatment choice at each decision time), this regime is consistent with the following four treatment paths: (1) if the patient responds favorable at both time points, they will experience Diet 1 repeated three times. (2) If they respond favorably at 3 months but not at 6 months, then their diet sequence would be Diet 1, Diet 1, and Diet 3. (3) If they responded unfavorably at 3 months but favorable at 6 months, then their diet sequence would be Diet 1, Diet 3, Diet 3. (4) If they respond unfavorably at both 3 and 6 months, their diet sequence would be Diet 1, Diet 3, and Diet 2. The issue is that a regime focuses on the decision a clinician can make either initially, or when the patient experiences an unfavorable response, at either 3 or 6 months. The remaining decisions are made automatically since favorable responses do not lead to changes in diet. Note that this means that some diet sequences are consistent with more than one treatment regime, and thus the data from same patients will sometimes be used for estimating more than one of the 12 regimes. With balanced randomization, at least 6 patients will be assigned to each treatment regime.

Moreover, we will in fact be able to make valid intent-to-treat comparisons across the three starting diets using the outcomes at 9 months, based on the fact the SMART designs have greater power for intent-to-treat hypotheses than traditional randomized designs (see Chapter 3 of Kosorok and Moodie, 2016). In a standard, randomized trial, failure of a diet would lead to either patient drop-out or switching of diet by the clinician. Thus two sources of bias arise: one from drop out and one from change in treatment. In contrast, with our design, we make additional diet assignments at 3 and 6 months based on diet success. We use randomization instead of ad hoc reassignment. Thus, our design more formally addresses both patient drop out and treatment changes by including diet changes in our design in a balanced way. There may still be some drop out, but it will be lower since patients do not have to leave the study to have their diet changed. Thus the design is adequate to achieve the stated objectives.

In addition, the Q-learning methodology will permit us to pool the data for regression models across similar branches among the possible treatment paths. To illustrate this, we point out that, as described in Chapter 17 of Kosorok and Moodie, 2016, Q-learning is done through a backwards iteration of regression model fitting, with different

regression models at each potential randomization point. In our setting, we can integrate the multiple possible regression models at the third decision time (6 months) into one regression model by including past diets in the history variables as well as by allowing for four treatment options, one for each of the three diets and one for those patients who stay on with the previous diet. We can similarly integrate across the regression models at the 3 month decision time and also at baseline, resulting in the need for only three regression models. We will therefore have sufficient power for all of our proposed analyses. In addition, we will have sufficient sample size to use the pilot data to sample size a full SMART design using the methods described by Laber et al., (2016).

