Following Measurement Visit 2, participants meeting one or more criteria for re-randomization will have the next diet in their individual randomized diet scheme revealed (one of two diets not yet experienced); otherwise, participants will continue their original diet assignment. Following Measurement Visit 3, decision criteria will be applied again. Participants meeting re-randomization criteria will have the next diet in their individual randomized diet scheme revealed (for participants who had continued on the original assignment at the 3-month mark, this will be one of the two remaining diets; for those who received a new diet, the only remaining untried diet will be assigned). By the end of the study, each participant will have either been on a diet that was acceptable and effective for a period of time or will have tried all 3 diets. For individuals assigned to one of the hypocaloric diets (low carbohydrate or Look AHEAD), at Measurement Visit 2 and/or Measurement Visit 3 the calorie prescription will be re-calculated to incorporate body weight and composition at that time. Note that at 3 and 6 months, if weight loss has been achieved that classifies participant as “normal weight” then ‘weight change’ criteria (see Table 7.1) does not apply for re-randomization. For these individuals, the RD will advise the participant regarding weight loss maintenance in the context of their assigned diet.

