**Table 7.1 Re-Randomization Criteria. Re-assignment of diet will occur if one or more criteria are met.**

Time post-initial randomization	Diet acceptability	Weight change	Glycemic control since baseline
3 and 6 months	Unacceptable based on Diet Acceptability Form	Not achieving at least 2% loss in body weight from previous measurement visit. Exception: if weight loss has been achieved that classifies participant as “normal weight” then this criteria does not apply	Self-report of increased hypoglycemia or HbA1c $\uparrow \geq 0.5\%$

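### Two power claims in Protocol section 11 are unsupported: sufficient power for all analyses contradicts the same section, and greater power at 9 months is unquantified and depends on the comparator

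*Protocol*

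**What the plan says.** Protocol section 11 makes the 3-month comparison of initial diets primary. For n = 84, significance level 0.10 and adjustment for multiple comparisons, it states 60% power at Cohen h = 0.68 and 80% at h = 0.85. It then adds "we have therefore not designed this pilot SMART to be fully powered for all analyses".

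Later in the section it says that valid intent-to-treat comparisons of starting diets can be made at 9 months, and rests this on the statement that "the SMART designs have greater power for intent-to-treat hypotheses than traditional randomized designs", citing a book chapter. The comparator is a standard trial in which "failure of a diet would lead to either patient drop-out or switching of diet by the clinician". On dropout it says only: "There may still be some drop out, but it will be lower since patients do not have to leave the study". The next paragraph, on Q-learning, ends: "We will therefore have sufficient power for all of our proposed analyses".

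Section 7 sets the reassignment. A participant who fails at 3 months receives "one of two diets not yet experienced". For one who fails again at 6 months, "the only remaining untried diet will be assigned". Any one criterion in Table 7.1 triggers a switch; the weight criterion is "Not achieving at least 2% loss in body weight from previous measurement visit", with an exception for participants who have reached normal weight.

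The SAP models change within each diet period. It lists no 9-month comparison by starting diet.

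**The concern.** There are two separate problems.

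1. The two general statements about power in section 11 cannot both stand. The section also proposes to compare all 12 diet sequences, with at least 6 participants assigned per regime.

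2. The greater-power claim has nothing quantitative behind it, and reassignment works against it. Failures go to the diets on which the other groups started, so the groups become more alike in the diets they receive. The inference also does not follow: an intent-to-treat comparison is valid because of randomization, not because of its power.

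The pilot exists to inform a fully powered SMART. A reader who takes the claim at face value could treat a null 9-month result as evidence that the diets do equally well, or carry an unearned power assumption into the next design.

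**Working it through.** **Stated power (3 months).** The protocol gives no 9-month power, so only the 3-month figures can be reproduced. I use the arcsine scale, two-sided, with alpha 0.10/3 = 0.0333 for three pairs (the form of adjustment and the sidedness are my assumptions). Power = Φ(h√(n/2) − 2.128).
- 28 per diet (84/3): 66.1% at h = 0.68 and 85.4% at h = 0.85.
- 24 per diet (72/3): 59.0% and 79.3%.

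The stated 60% and 80% therefore match the 72 that the SAP calls planned, not 84. Either way, the primary comparison has only about 60% to 66% power at the moderate effect.

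**9-month contrast.** Inputs from Protocol sections 7 and 11: failures are split equally over untried diets, with no return to a failed diet. Assumptions, because the documents give no values: a common response probability p at 3 and 6 months, equal additive effects per period, no dropout.

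*Outcome that accumulates over the three periods (weight).* Expected periods on Diet 1:
- Starting on Diet 1: 3p² + 2p(1−p) + (1−p) = 1 + p + p².
- Starting on Diet 2: paths (2,2,1), (2,1,1), (2,1,3) and (2,3,1) give 1.5p(1−p) + (1−p)² = (1−p)(2+p)/2.
- Difference: 1.5p(1+p), against 3 without switching. Fraction kept: p(1+p)/2.

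If the trial without switching has 80% power, its standardized effect is 1.645 + 0.842 = 2.486 at two-sided alpha 0.10, or 2.128 + 0.842 = 2.970 at 0.10/3. Multiply by the fraction kept, subtract the critical value, and add the small opposite tail:

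| p | Contrast kept | Power, alpha 0.10 | Power, alpha 0.10/3 |
|---|---|---|---|
| 0.3 | 19.5% | 14% | 6% |
| 0.5 | 37.5% | 24% | 16% |
| 0.7 | 59.5% | 44% | 36% |

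With unequal response (0.6 on the better diet, 0.3 on the other two), expected periods on the better diet are 1.96 when starting on it and 0.91 otherwise. The contrast kept is (1.96 − 0.91)/3 = 35%, and power is about 22% at alpha 0.10.

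*Outcome set by the current diet.* The probability of being on Diet 1 in the last period is p² when starting on it and (1−p²)/2 when starting on Diet 2. The fraction kept is (3p²−1)/2: 23.5% at p = 0.7 and −12.5% at p = 0.5. It changes sign at p = √(1/3), about 0.58.

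**Is a low p plausible?** Section 9a aims the hypocaloric diets at 7% loss in a year. If linear, that is 7/4 = 1.75% in 3 months or 7 × 3.5/12 = 2.04% in 3.5 months. A participant exactly on target sits close to the 2% line in Table 7.1. This shows only that failure could be common; it gives no rate.

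**Against the protocol's own comparator.** A simulation used 24 per arm, the 2% threshold, alpha 0.10/3 and total loss over three periods. Assumed mean losses per period were 2.5/1.3/1.3% or 3.5/2.3/2.3%, with participant-by-diet and residual SDs of 1.2 each, and 700 runs (standard error up to about 2 points).

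| Design | Failure rate about 0.5 | Failure rate about 0.3 |
|---|---|---|
| All stay on assigned diet, full follow-up | 78% | 78% |
| SMART | 23% | 44% |
| Clinician switches all failures | 20% | 42% |
| Half switched, half drop out | 28% | 41% |
| All failures drop out, completers analysed | 9% | 22% |

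**The case against.** The strongest defence is that the protocol does not compare itself with a trial in which everyone stays on the assigned diet. Its standard trial also loses or switches its failures. Against that trial the simulated SMART is about equal where failures are switched, and better where they all drop out. The cited chapter cannot be checked here. This stands, and it rules out calling the greater-power claim simply wrong. It does not establish the claim either: the ranking depends on assumptions. A simpler calculation that ignores selection on response, and only shrinks the sample for dropout, favours the dropout-only trial over the SMART (47% against 35% at failure rate 0.3).

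It is also fair to say that a comparison of strategies beginning with each diet is a legitimate intent-to-treat question, and that the protocol does not claim to estimate the effect of staying on a diet. The power figures above rest on a p that the documents never state.

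Finally, the sufficiency sentence closes the Q-learning paragraph, and the crossover arithmetic does not bear on Q-learning. That is correct. The objection to that sentence is its conflict with the earlier disclaimer; it refers to all proposed analyses, so its position does not resolve the conflict.

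**Conclusion.** The contradiction between the two general power statements is established by the text and needs no modelling.

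The greater-power claim is unsupported. Under the stated assumptions it is false against a fixed-diet trial with full follow-up, with 20% to 60% of the contrast kept for an accumulating outcome at p from 0.3 to 0.7. Against the comparator that the protocol describes, the answer depends on failure, switching and dropout rates that it does not give.

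A reader might infer more than this, and three such readings do not hold:
- That the claim is wrong outright, or that the 9-month comparison is invalid. Randomization keeps it valid as a comparison of strategies.
- That switching always shrinks the contrast toward zero or removes most of it. At p = 0.7 an accumulating outcome keeps about 60%, and an outcome set by the current diet can reverse sign.
- That the main results are compromised. The 3-month comparison precedes any reassignment, and the SAP models change by diet period.

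**What to change.** In Protocol section 11:
- Delete the sentence claiming sufficient power for all proposed analyses, or restate it to agree with the earlier disclaimer.
- Remove the greater-power claim. Alternatively, name its comparator and give the assumed failure and dropout rates and the resulting 9-month power.
- Rest the validity of the 9-month comparison on randomization. State that it estimates the effect of strategies beginning with each diet, that it is exploratory with no claimed power, and that a null result is not evidence that the diets are equivalent.
- State that the 3-month comparison is the one the design was sized for.

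The cost is wording only. No analysis changes; the stated power position becomes less favourable. If 9-month power is to be claimed, a short calculation with declared rates is needed.
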